#### **7.2.2.2. Adverse Events of Special Interest**

In the event of a non-serious AESI, the investigator must complete the AESI report form and send it to the Sponsor/designee immediately, within 24 hours. Names, addresses, and telephone and fax numbers for AESI reporting will be included on the report form. Serious AESIs must be reported in an expedited manner as SAEs, as outlined above.

#### **7.2.2.3. Safety Reporting to Health Authorities, Independent Ethics Committees/ Institutional Review Boards, and Investigators**

The Sponsor will send appropriate safety notifications to health authorities in accordance with applicable laws and regulations.

The investigator must comply with any applicable site-specific requirements related to reporting of SAEs (and in particular deaths) involving his/her subjects to the IEC/IRB that approved the trial.

In accordance with International Conference on Harmonization Good Clinical Practice (GCP) guidelines, the Sponsor or designee will inform the investigator of "findings that could adversely affect the safety of subjects, impact the conduct of the trial, or alter the IEC's/IRB's approval/favorable opinion to continue the trial." In accordance with respective regulations, the Sponsor or designee will inform the investigator of AEs that are both serious and unexpected, and are considered to be related to the administered product (suspected unexpected serious adverse reactions [SUSARs]). The investigator should place copies of safety reports in the

investigator site file. National regulations with regard to safety report notifications to investigators will be taken into account.

When specifically required by regulations and guidelines, the Sponsor or designee will provide appropriate safety reports directly to the concerned health authority and lead IEC/IRB, and will maintain records of these notifications. When direct reporting by the Sponsor or designee is not clearly defined by national or site-specific regulations, the investigator will be responsible for promptly notifying the concerned IEC/IRB of any safety reports provided by the Sponsor or designee, and for filing copies of all related correspondence in the investigator site file.

### **7.3. Monitoring of Subjects with Adverse Events**

Adverse events are recorded and assessed continuously throughout the trial starting at the time the subject receives his/her first treatment ([Section 7.2.1](#)) and are assessed for final outcome at the end-of-treatment visit.

After the End-of-Treatment Safety Follow-up Visit, only treatment-related AEs will be documented through the Treatment Follow-up Period of up to 12 months after the last dose of study drug or until disease progression and/or initiation of a new line of therapy.

All SAEs ongoing at the post-treatment safety follow-up visit must be monitored and followed by the investigator until stabilization or until the outcome is known, unless the subject is documented as “lost to follow-up.”

Reasonable attempts to obtain this information must be made and documented. It is also the responsibility of the investigator to ensure that any necessary additional therapeutic measures and follow-up procedures are performed.

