#### **6.3.3.2. Safety Follow-up Visit**

The mandatory Safety Follow-Up Visit should be conducted for all subjects approximately 4 weeks after the last dose of study drug or before the initiation of a new antineoplastic treatment, whichever comes first. Subjects with an AE of Grade >1 will be further followed until the resolution of the AE to Grade 0-1 or until beginning of a new antineoplastic therapy, whichever occurs first. Subjects with an adverse drug reaction (ADR) ongoing at the Safety Follow-up Visit must be followed up until the ADR resolves, becomes stable, or is considered not clinically significant by the investigator.

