### 7.2.1. Definition of the Adverse Event Reporting Period

The AE reporting period for safety surveillance begins when the subject provides written consent and continues until either 90 days after the last dose of study drug or the start of new anticancer treatment, whichever comes first. Following the End-of-Treatment Safety Follow-up Visit, only treatment-related AEs will be documented through the Treatment Follow-up Period of up to 12 months after the last dose of study drug or until disease progression and/or initiation of a new line of therapy, whichever comes first.

Any SAE suspected to be related to trial treatment must be reported whenever it occurs, irrespective of time elapsed since last dose of study drug.

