The median duration of TEAE (in days) will be calculated using Kaplan Meier analysis for all patients and AE included in a cluster. Unresolved AEs or AEs with missing resolution information and date will be treated as censored data with the end of extended on-treatment period as censoring date.

Death summary table will present reasons for deaths on treatment period, in survival follow-up, and overall.

Death details will also be listed (if applicable) including:

- Number of doses of balstilimab
- Number of cycles

- Age at death
- Study days relative to first dose date, calculated as (death date – first dose date + 1)
- Number of days to death from last dose, calculated as (death date – last dose date + 1)
- Precipitating AE (if death is an outcome of AE)
- Immune-related AE (if death is an outcome of irAE per investigator)
- Cause of deaths

The following listings will be provided in Safety Analysis Set:

- All AEs (with TEAEs flagged)
- Related TEAEs
- Serious TEAEs
- TEAEs leading to treatment discontinuation
- TEAEs leading to death
- Death details (including age, study day, and days from last dose, AEs, and death cause).

Adverse events observed between signing the informed consent and first dose of study drug will be listed with negative study days.

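### Protocol 7.3 conflicts with 7.2.1 and 6.3.3.2 on when AE recording starts and follow-up ends, and SAP 7.6.2 censors unresolved cluster AEs later than they may have been observed, so Kaplan-Meier AE durations can be biased long

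*Protocol*

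**What the plan says.** **Start of recording.** Protocol 7.3 has AEs recorded "starting at the time the subject receives his/her first treatment" and refers to 7.2.1 for this. In 7.2.1 the reporting period "begins when the subject provides written consent and continues until either 90 days after the last dose of study drug", or until new anticancer treatment if that is sooner. Protocol 6.4.3.1 and Table 13 footnote 5 also start at consent.

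**End of follow-up.** The same sentence of 7.3 says AEs "are assessed for final outcome at the end-of-treatment visit". The section then makes two exceptions. After the safety visit, "only treatment-related AEs will be documented through the Treatment Follow-up Period of up to 12 months" after the last dose, and ongoing SAEs "must be monitored and followed by the investigator until stabilization or until the outcome is known". Protocol 6.3.3.2 is wider: "Subjects with an AE of Grade >1 will be further followed until the resolution of the AE to Grade 0-1", or until a new antineoplastic therapy begins. It also follows ongoing adverse drug reactions until they resolve, stabilise or are judged not clinically significant.

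**Analysis.** Duration of TEAEs is part of a Phase 2 secondary endpoint (Protocol 2.1.2, SAP 3.5). SAP 7.6.2 estimates median duration by Kaplan-Meier within clusters of immune-mediated AEs, which it defines by lists of MedDRA Preferred Terms. "Unresolved AEs or AEs with missing resolution information and date will be treated as censored data with the end of extended on-treatment period" as the censoring date. SAP 5.4 sets that date at 90 days after the last dose, or end of study if earlier. AEs between consent and first dose are only listed, with negative study days.

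**The concern.** Two separate matters meet here.

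The first is a conflict within the protocol. A site that works from 7.3 alone could leave out AEs that arise between consent and first dose. It could also close the outcome of a non-serious, unrelated AE above Grade 1 at the end-of-treatment visit, when 6.3.3.2 would have kept it under follow-up.

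The second is a SAP convention. Kaplan-Meier censoring should fall on the last date at which the AE was known to be ongoing. The SAP uses a fixed later date. If follow-up stopped before that date, the AE stays in the risk set over a stretch in which its resolution could not have been recorded. The risk set is too large for the events counted, and the estimated duration moves up. The percentage resolved, also reported for each cluster, moves down whenever a resolution goes unrecorded.

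**Working it through.** **Step 1. Passages side by side.** The documents state no figure on this point, so there is none to reproduce.

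| Question | Protocol 7.3 | Other passages |
|---|---|---|
| Start of recording | First treatment (citing 7.2.1) | Consent (7.2.1, 6.4.3.1, Table 13 footnote 5) |
| Ongoing SAE at safety visit | Followed until stable or outcome known | No conflict |
| Ongoing treatment-related AE | Documented up to 12 months | Followed under 6.3.3.2; no material conflict |
| Ongoing non-serious, unrelated AE above Grade 1 | Outcome assessed at end-of-treatment visit | Followed to Grade 0-1 or new therapy (6.3.3.2) |

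Only the first and last rows conflict.

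**Step 2. Do the affected AEs reach the duration analysis?** Yes. The clusters are built from Preferred Terms such as diarrhoea, rash and pruritus, not from causality, so events judged unrelated enter them.

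**Step 3. When can follow-up stop before the censoring date?**

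- If 7.3 is followed, at the safety visit about 4 weeks after last dose. The gap is 90 - 28 = 62 days, or with the ±7-day window 90 - 35 = 55 to 90 - 21 = 69 days.
- If 7.2.1 and 6.3.3.2 are followed in full, at new anticancer therapy, or once the AE has fallen to Grade 1. SAP 5.4 has no cutoff at new therapy, so the gap also arises at a compliant site.
- For a subject dosed shortly before the 11 Feb 2021 cutoff (SAP 4.2), last dose plus 90 days falls after the cutoff.

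**Step 4. Size.** Assumptions that are not in the documents: exponential durations with median m (mean m / ln 2), onset uniform from 84 days before to 28 days after last dose, and a stated share of AEs whose status is last seen at day c after last dose. The others are followed to day 90. An AE counts as resolved if onset + duration falls on or before its last-seen day. Otherwise it is censored at 90 - onset (SAP rule) or at last-seen day - onset (proposed rule).

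| Scenario | True median 28 days | True median 56 days |
|---|---|---|
| 20% last seen at day 28, SAP rule | about 29 | about 60 |
| 50% last seen at day 28, SAP rule | about 31 | about 70 |
| 30% to 50% start new therapy at day 35, SAP rule | about 29 | about 60 to 65 |
| All last seen at day 28, SAP rule (worst case) | about 35 | not reached |
| Any of these, censored at last-seen day | 28 | 56 |

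A variant with onset uniform from first dose to 28 days after last dose, last dose at day 84 or 180, and 20% last seen at day 28 gives 14 to 14, 30 to 31, and 60 to 62-65 days. The shift is never downward, and it is small for short AEs.

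**The case against.** The case against giving this much weight is good, and most of it stands.

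- A reader might infer that 7.3 closes every AE at the end-of-treatment visit and that AE durations are therefore biased long in general. The documents do not support that. The later paragraphs of 7.3 keep SAEs and treatment-related AEs under follow-up, and the Kaplan-Meier rule is written for the immune-mediated clusters only.
- All subjects who discontinue treatment have a visit 3 months after last dose, and Table 13 schedules AE review there, close to the SAP's censoring date. Suspected immune-mediated AEs are also AESIs, reportable for 90 days (or to 30 days after new anticancer therapy, if earlier) regardless of attribution (Protocol 7.1.8). Freezing every outcome at day 28 is therefore not a realistic expectation.
- A reader might take the apparent absence of a screening mark in the AE-review row of Table 13 as a second gap. That is weak evidence. The table's columns are unreliable as extracted, and footnote 5, attached to that row, requires recording from consent.
- Pre-dose AEs do not enter TEAE counts by onset.

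Two things survive. The first sentence of 7.3 contradicts the section it cites and also 6.3.3.2. And the censoring date is wrong in principle whether or not any site follows 7.3, because follow-up may properly stop at new therapy while the SAP goes on counting the AE as unresolved.

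**Conclusion.** The point holds in a limited form. Protocol 7.3 needs reconciling on both the start and the end of follow-up. The first affects the completeness of the pre-dose AE listing. The second affects only non-serious AEs judged unrelated that are ongoing at the visit.

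The SAP censoring rule can bias cluster durations upward. The likely size is small for AEs lasting a few weeks (28 days becomes about 29 to 31) and moderate for those lasting around two months (56 becomes about 60 to 70). These figures rest on assumed exponential durations, uniform onset and an assumed share of truncated follow-up. The documents give no basis for choosing that share, so the direction is firmer than the amount. Nothing here touches the primary endpoint or TEAE onset counts.

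**What to change.** 1. **Protocol 7.3, first sentence.** Reconcile it with 7.2.1 on when recording starts and with 6.3.3.2 on how long AEs are followed. This is a change of wording only and adds no visits beyond those already required.

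2. **SAP 7.6.2.** Censor unresolved AEs at the last date on which the AE's status was documented, or at the last AE-review visit if the eCRF collects no such date. Censoring should be no later than the earliest of new anticancer therapy (where follow-up stops there), data cutoff, end of study, and last dose plus 90 days.

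The cost is slightly earlier censoring and a small programming change. The eCRF is not among the documents, so whether a status date is collected has to be checked; the visit-based fallback covers the case where it is not.

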### **7.4. Pregnancy and In Utero Drug Exposure**

Only pregnancies considered by the investigator as related to trial treatment (e.g., resulting from a drug interaction with a contraceptive medication) are considered as AEs.

However, all pregnancies with an estimated conception date during the period defined in [Section 7.2.1](#) must be recorded by convention in the AE page/section of the eCRF.

The same rule applies to pregnancies in female subjects and in female partners of male subjects. The investigator must notify the Sponsor or designee in an expedited manner of any pregnancy using the pregnancy report form, which must be transmitted according to the same process as described for SAE reporting in [Section 7.2.2](#).

Investigators must actively follow up, document, and report the outcome of these pregnancies, even if subjects are withdrawn from the trial. A separate consent will be obtained for follow-up of these subjects.

The investigator must notify the Sponsor or designee of these outcomes using the pregnancy report form and, in case of abnormal outcome, the SAE report form if the subject sustains an event and the parent-child/fetus AE report form when the child/fetus sustains an event).

Any abnormal outcome must be reported in an expedited manner, as described in [Section 7.2.2](#), whereas normal outcomes must be reported within 45 days from delivery.

In the event of a pregnancy in a subject occurring during the course of the trial, the subject must be discontinued from trial medication immediately. The Sponsor or designee must be notified without delay and the subject must be followed as described above.

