9. Female subjects must have a negative serum pregnancy test at screening (within 72 hours before first dose of study drug) if of childbearing potential or be of non-child bearing potential. Non-childbearing potential is defined as (by other than medical reasons):
  - a.  $\geq 45$  years of age and has not menstruated for greater than 1 year,
  - b. Amenorrheic for  $< 2$  years without a hysterectomy and oophorectomy and a follicle-stimulating hormone (FSH) value in the postmenopausal range upon pretrial (screening) evaluation,
  - c. Whose status is post hysterectomy, oophorectomy or tubal ligation.
10. If of childbearing potential, female subjects must be willing to use 2 highly effective methods (defined in the informed consent form [ICF]) throughout the study, starting with the screening visit through 120 days after the last dose of study drug.  
**Note:** Abstinence is acceptable if this is the established and preferred contraception for the subject.
11. Male subjects with a female partner(s) of child-bearing potential must agree to use 2 highly effective methods (defined in the ICF) throughout the trial starting with the screening visit through 120 days after the last dose of study drug is received. Males with pregnant partners must agree to use a condom; no additional method of contraception is required for the pregnant partner.  
**Note:** Abstinence is acceptable if this is the established and preferred contraception for the subject.
12. Is willing and able to comply with the requirements of the protocol.

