16. Has a history or current evidence of any condition, therapy, or laboratory abnormality that might confound the results of the trial, interfere with the subject's participation for the full duration of the trial, or is not in the best interest of the subject to participate, in the opinion of the treating Investigator.
17. Has known psychiatric or substance abuse disorders that would interfere with cooperation with the requirements of the trial.
18. Is, at the time of signing informed consent, a regular user (including "recreational use") of any illicit drugs or had a recent history (within the last year) of substance abuse (including alcohol).
19. Is legally incapacitated or has limited legal capacity.
20. Is pregnant or breastfeeding or expecting to conceive or father children within the projected duration of the trial, starting with the screening visit through 120 days after the last dose of study drug.

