#### **7.1.8. Predefined Potential AEs of Special Interest for Safety Monitoring**

Selected non-serious and SAEs defined below are considered AESIs and must be recorded as such on the Adverse Event case report forms/worksheets and reported within 24 hours to the Sponsor either by electronic media or paper. Sponsor Contact information can be found in the Investigator Trial File Binder (or equivalent).

Events of clinical interest for this trial include:

- Infusion-related reactions.
- An elevated AST or ALT lab value that is greater than or equal to 3X the upper limit of normal and an elevated total bilirubin lab value that is greater than or equal to 2X the upper limit of normal and, at the same time, an alkaline phosphatase lab value that is less than 2X the upper limit of normal, as determined by way of protocol-specified laboratory testing or unscheduled laboratory testing.

Note: These criteria are based upon available regulatory guidance documents. The purpose of the criteria is to specify a threshold of abnormal hepatic tests that may require an additional evaluation for an underlying etiology. The trial site guidance for assessment and follow up of these criteria can be found in [Section 5.6.4](#).

- Any AE that is reasonably suspected to be immune-mediated (ie, an irAE).

AESIs (both non-serious and serious AEs) identified in this guidance document from the date of first dose through 90 days following cessation of treatment, or 30 days after the initiation of a new anticancer therapy, whichever is earlier, need to be reported to the SPONSOR within 24 hours of the event, regardless of attribution to study treatment, consistent with standard SAE reporting guidelines and either by electronic media or paper.

Subjects should be assessed for possible AESIs prior to each dose. Lab results should be evaluated and subjects should be asked for signs and symptoms suggestive of an immune-related event. Subjects who develop an AE thought to be immune-related should have additional testing to rule out other etiologic causes. If lab results or symptoms indicate a possible irAE, then additional testing should be performed to rule out other etiologic causes. If no other cause is found, then it is assumed to be immune-related.

Any infusion reaction, regardless of Grade, must be reported in an expeditious manner and will be considered an AESI. The reporting of AESI is described in [Section 7.2.2](#).

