## 7.2. Methods of Recording and Assessing Adverse Events

At each trial visit, the subject will be queried on changes in his/her condition. During the reporting period of the trial, any unfavorable changes in the subject's condition will be recorded as AEs, whether reported by the subject or observed by the investigator.

Complete, accurate, and consistent data on all AEs experienced for the duration of the reporting period (defined below) will be reported on an ongoing basis in the appropriate section of the eCRF. Among these AEs, all SAEs and all non-serious AESIs must be additionally documented and reported using the appropriate report form as described in Section 7.2.2.

It is important that each AE report include a description of the event, its duration (onset and resolution dates and times to be completed when it is important to assess time of AE onset relative to recorded treatment administration time), its severity, causal relationship with trial treatment, any other potential causal factors, any treatment administered or other action taken (including dose modification or discontinuation of study drug), and outcome. In addition, serious cases should be identified and the appropriate seriousness criteria documented.

Specific guidance can be found in the eCRF Completion and Monitoring Conventions.

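### The mandatory pregnancy-recording period (90 days after last dose, or new anticancer therapy) is shorter than the protocol's own 120-day contraception window, and the protocol and SAP disagree on whether new therapy ends collection of immune-related events

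*Protocol*

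**What the plan says.** **Pregnancy.** Protocol Section 7.4 asks sites to enter on the AE page of the eCRF "all pregnancies with an estimated conception date during the period defined in" Section 7.2.1. Under Section 7.2.1 the AE reporting period begins at consent and "continues until either 90 days after the last dose of study drug or the start of new anticancer treatment, whichever comes first". Section 7.4 then extends the same rule to female partners of male subjects, requires expedited notification of any pregnancy on the pregnancy report form, and requires active follow-up of outcomes, including after withdrawal.

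The eligibility criteria use a longer window. Inclusion criteria 10 and 11 require contraception "starting with the screening visit through 120 days after the last dose of study drug". Exclusion criterion 20 bars subjects "expecting to conceive or father children within the projected duration of the trial", again to 120 days after the last dose. Neither stops at new anticancer therapy.

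**AESIs, including suspected immune-related AEs (irAEs).** Section 7.1.8 says they "must be recorded as such on the Adverse Event case report forms/worksheets". They are reportable within 24 hours, "regardless of attribution to study treatment", from first dose "through 90 days following cessation of treatment, or 30 days after the initiation of a new anticancer therapy, whichever is earlier". Section 7.2 describes recording of AEs during the reporting period and adds: "Among these AEs, all SAEs and all non-serious AESIs must be additionally documented". Table 13 footnote 5 repeats the Section 7.2.1 cut-off for Phase 2. SAP Section 5.4 defines the extended on-treatment period, used for irAEs, as running to 90 days after the last dose or end of study. It has no new-therapy cut-off.

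**The concern.** A recording rule for pregnancies would normally cover at least the period in which the protocol itself asks subjects to avoid conception. Here it is borrowed from the general AE period, which is shorter and also closes when another anticancer drug starts. The start of another drug says nothing about exposure to AGEN2034 already given. A site following the Section 7.4 conception-date rule literally could decide that a conception inside the contraception window need not be entered.

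For AESIs the concern is one of conflicting instructions. A suspected irAE shortly after new therapy is to be recorded under Section 7.1.8, but it lies after the end of the period that Sections 7.2 and 7.2.1 describe. Sites may resolve this differently. The SAP then analyses irAEs to day 90 as though collection continued to that day for everyone.

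**Working it through.** There is no stated figure to reproduce; this is a comparison of windows. Days are counted from the last dose, and T is the day new anticancer therapy starts. I take cessation of treatment in Section 7.1.8 to be the day of the last dose.

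Inputs:
- End of the AE period, which also governs pregnancy recording (Sections 7.2.1 and 7.4): min(90, T).
- End of the contraception and conception window (inclusion 10 and 11, exclusion 20): 120.
- End of the AESI window (Section 7.1.8): min(90, T + 30).
- End of the irAE analysis window (SAP Section 5.4): 90, if the subject is still on study.

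Formulas:
- Pregnancy gap = 120 − min(90, T).
- Conflict between Sections 7.1.8 and 7.2.1 = min(90, T + 30) − min(90, T), which is min(30, 90 − T) for T < 90 and 0 otherwise.
- Days analysed under SAP Section 5.4 after the AESI window closes = 90 − min(90, T + 30), which is 60 − T for T < 60 and 0 otherwise.

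| New therapy starts | 7.2.1 ends | Pregnancy gap (days) | 7.1.8 ends | 7.1.8 vs 7.2.1 (days) | SAP 5.4 beyond 7.1.8 (days) |
|---|---|---|---|---|---|
| Not before day 90 | 90 | 30 | 90 | 0 | 0 |
| Day 75 | 75 | 45 | 90 | 15 | 0 |
| Day 60 | 60 | 60 | 90 | 30 | 0 |
| Day 45 | 45 | 75 | 75 | 30 | 15 |
| Day 28 | 28 | 92 | 58 | 30 | 32 |
| Day 14 | 14 | 106 | 44 | 30 | 46 |

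The pregnancy gap is always at least 30 of the 120 days (25%) and reaches 92 of 120 (77%) when T = 28. The AESI conflict exists only when new therapy starts before day 90 and never exceeds 30 days.

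Other collection routes:
- Section 7.2.1 documents treatment-related AEs for up to 12 months, but only until progression or new therapy, so it does not help after day T.
- Section 7.2.1 also requires related SAEs whenever they occur. That covers serious drug-related irAEs at any time.
- Between T + 30 and day 90, with T < 60, this leaves non-serious irAEs with no collection instruction although the SAP analyses that interval.

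**The case against.** **Notification of any pregnancy.** This sentence in Section 7.4 carries no stated time limit, and outcome follow-up is mandatory. On that reading a conception on day 100 is still notified and followed, and only the AE-page entry is limited. A reader might infer from the mismatch that in utero exposures go uncollected without outcome follow-up. The documents do not support that. Nor do they settle the matter the other way: the sentence sits between one extending the conception-date rule to partners and one requiring follow-up of the pregnancies just described, so a site could take all of it to be bounded by Section 7.2.1. The ambiguity stands.

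**AESIs.** A reader might also infer that late immune events fall outside collection, or that the AESI window is generally the longer one. Neither is right. Section 7.1.8 puts AESIs on the AE form in its own right, its window is capped at day 90, and it matches Section 7.2.1 unless new therapy starts earlier. Events recorded under Section 7.1.8 would enter the SAP irAE analysis, so it does not follow that the tables lose events sites were asked to report. What stands is a conflict between sections and the smaller shortfall against SAP Section 5.4.

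**Size of the exposure.** With the preliminary half-life of about 10 days (Section 1.2.2) and simple exponential decline, 2^(−9) ≈ 0.2% of the drug remains at day 90, so the fixed gap on days 91 to 120 carries little residual drug. At day 28 the figure is 2^(−2.8) ≈ 14%, relevant only to subjects who switch that early. The finding rests on the protocol's own 120-day window, not on these figures.

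**Practical weight.** Phase 1 enrolment is complete, Phase 2 enrols advanced cervical cancer, few pregnancies are expected, and the primary endpoint is untouched. This is fair, and it limits the priority of the point without removing the inconsistency.

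**Conclusion.** The pregnancy point holds as an internal inconsistency. Mandatory eCRF recording stops at least 30 days before the protocol's contraception window ends, and 120 − T days before it when new therapy starts on day T < 90. The notification sentence is too unclear to close that gap. The documents do not show that any pregnancy would actually be missed.

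The secondary point holds in a narrow form. After new therapy before day 90, Section 7.1.8 conflicts with Sections 7.2 and 7.2.1 and Table 13 footnote 5 for min(30, 90 − T) days. For T < 60, SAP Section 5.4 analyses irAEs for a further 60 − T days beyond the Section 7.1.8 window.

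The size in practice depends on how many subjects conceive and how many switch before day 90. The documents give neither, so the working shows a range of T and makes no estimate of affected subjects. I take no position on how long contraception should last.

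**What to change.** 1. In Section 7.4, reconcile the recording and outcome follow-up period with the 120-day window in inclusion criteria 10 and 11 and exclusion criterion 20, independent of new anticancer therapy. State that the duty to notify any pregnancy covers that same window. This brings the pregnancy gap to 0 days and leaves the contraception requirement as written.
2. In Section 7.2.1 and Table 13 footnote 5, state that AESIs are recorded on the AE form for the full Section 7.1.8 window, together with the start date of any new therapy.
3. Reconcile Section 7.1.8 with SAP Section 5.4. One option is for the SAP to flag or censor irAE follow-up at the point where collection stops before day 90.

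The cost is a few sentences in the protocol, the SAP and the eCRF completion guidance, plus a little extra reporting. Actively finding conceptions on days 91 to 120 may need an added question at existing contacts: the last scheduled pregnancy test in Table 13 is at the 3-month visit, after which Phase 2 subjects with progression or new therapy are telephoned every 2 months. Phase 1 has no survival follow-up, so for Phase 1 subjects whose participation ends at the 3-month visit, recording would depend on what the subject or site reports.
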